6. SAFETY REPORTING AND MEDICAL MANAGEMENT

The Principal Investigator is responsible for ensuring that all staff involved in the study is familiar with the content of this section.

6.1 Definition of adverse events

An AE is the development of an undesirable medical condition (other than progression of the malignancy under evaluation) or the deterioration of a pre-existing medical condition following or during exposure to a pharmaceutical product, whether or not considered causally related to the product. An undesirable medical condition can be symptoms (eg, nausea, chest pain), signs (eg, tachycardia, enlarged liver) or the abnormal results of an investigation (eg, laboratory findings, ECG). In clinical studies, an AE can include an undesirable medical condition occurring at any time, including run-in or washout periods, even if no study treatment has been administered.

The term AE is used to include both serious and non-serious AEs.

6.2 Definitions of serious adverse event

A SAE is an AE occurring during any study phase (ie, run-in, treatment, washout, and follow up), that fulfills one or more of the following criteria:

- Results in death
- Is immediately life-threatening
- Requires in-patient hospitalization or prolongation of existing hospitalization
- Results in persistent or significant disability/incapacity or substantial disruption of the ability to conduct normal life functions
- Is a congenital abnormality or birth defect
- Is an important medical event that may jeopardize the patient or may require medical intervention to prevent one of the outcomes listed above

•

AEs for new malignant tumors (ie, not the tumor for which entry into the study is a criterion and that is being treated by the IP under study and is not the development of new or progression of existing metastasis to the tumor under study) reported during a study should generally be assessed as SAEs. If no other seriousness criteria apply, the 'Important Medical Event' criterion should be used.

In certain situations, however, medical judgement on an individual event basis should be applied to clarify that the malignant tumor event should be assessed and reported as a non-serious AE. For example, if the tumor is included as medical history and progression occurs during the study, but the progression does not change treatment and/or prognosis of the malignant tumor, the AE may not fulfill the attributes for being assessed as serious, although reporting of the progression of the malignant tumor as an AE is valid and should occur. Also, some types of malignant tumors, which do not spread remotely after a routine treatment that does not require hospitalization, may be assessed as non-serious; examples include Stage 1 basal cell carcinoma and Stage 1A1 cervical cancer removed via cone biopsy.

Malignant tumors that – as part of normal, if rare, progression – undergo transformation (eg, Richter's transformation of B cell chronic lymphocytic leukemia into diffuse large B cell lymphoma) should not be considered a new malignant tumor.

For further guidance on the definition of a SAE, see Additional Safety Information in APPENDIX A.

6.3 Recording of adverse events

6.3.1 Time period for collection of adverse events

Adverse events and SAEs will be collected from time of the patient signing the ICF until the follow up period is completed (90 days after the last study treatment administration). If an event that starts post the defined safety follow up period noted above is considered to be due to a late onset toxicity to study drug then it should be reported as an AE or SAE as applicable.

6.3.2 Follow up of unresolved adverse events

During the course of the study, all AEs and SAEs should be proactively followed up for each patient for as long as the event is ongoing. Every effort should be made to obtain a resolution for all events, even if the events continue after the patient has discontinued study drug or the study has completed.

Any AEs that are unresolved at the patient's last visit in the study are followed up by the Investigator for as long as medically indicated, but without further recording in the CRF. AstraZeneca retains the right to request additional information for any patient with ongoing AE(s)/SAE(s) at the end of the study, if judged necessary.

6.3.3 Variables

The following variables will be collected for each AE:

- AE (verbatim)
- The date when the AE started and stopped
- The maximum CTCAE grade reported
- Changes in CTCAE grade (report only the maximum CTCAE grade for a calendar day)
- Whether the AE is serious or not
- Investigator causality rating against the IPs (yes or no)
- Action taken with regard to IPs
- Administration of treatment for the AE
- Outcome

In addition, the following variables will be collected for SAEs:

- Date the AE met criteria for SAE
- Date the Investigator became aware of the SAE
- Seriousness criteria
- Date of hospitalization
- Date of discharge
- Probable cause of death
- Date of death
- Whether an autopsy was performed
- Causality assessment in relation to study procedure(s)
- Causality assessment in relation to other medication, as explained in Section 6.3.4
- Description of the SAE

The grading scales found in the revised NCI CTCAE version 4.03 will be utilized for all events with an assigned CTCAE grading. For those events without assigned CTCAE grades, the recommendation in the CTCAE criteria that converts mild, moderate, and severe events into CTCAE grades should be used. A copy of the CTCAE version 4.03 can be downloaded from the Cancer Therapy Evaluation Program website (http://ctep.cancer.gov).

It is important to distinguish between serious and severe AEs. Severity is a measure of intensity whereas seriousness is defined by the criteria in Section 6.2 and the Additional Safety Information in APPENDIX A. An AE of severe intensity need not necessarily be considered serious. For example, nausea that persists for several hours may be considered severe nausea, but not a SAE unless it meets the criteria shown in Section 6.2 and APPENDIX A. On the other hand, a stroke that results in only a limited degree of disability may be considered a mild stroke but would be a SAE when it satisfies the criteria shown in Section 6.2 and APPENDIX A.

6.3.4 Causality collection

The Investigator will assess causal relationship between durvalumab (monotherapy Modules), or between durvalumab and tremelimumab (combination therapy Modules) and each AE, and answer 'yes' or 'no' to the question 'Do you consider that there is a reasonable possibility that the event may have been caused by durvalumab?' (monotherapy Modules) or and 'Do you consider that there is a reasonable possibility that the event may have been caused by durvalumab?' (monotherapy Modules) or and 'Do you consider that there is a reasonable possibility that the event may have been caused by durvalumab?' (combination therapy Modules)?'

For SAEs, causal relationship will also be assessed for other medication, study procedures and alternative etiologies. Note that for SAEs that could be associated with any study procedure the causal relationship is implied as 'yes'.

A guide to the interpretation of the causality question is found in APPENDIX A.

6.3.5 Relationship to protocol procedures

The Investigator is also required to provide an assessment of the relationship of SAEs to protocol procedures on the SAE report form. This includes both non-treatment-emergent (ie, SAEs that occur prior to the administration of IP) and treatment-emergent SAEs. A protocol-related SAE may occur as a result of a procedure or intervention required during the study (eg, blood collection). The following guidelines should be used by Investigators to assess the relationship of SAEs to the protocol:

- Protocol-related: The event occurred due to a procedure or intervention that was described in the protocol for which there is no alternative etiology present in the patient's medical record.
- Not protocol-related: The event is related to an etiology other than the procedure or intervention that was described in the protocol. The alternative etiology must be documented in the study patient's medical record.

6.3.6 Adverse events based on signs and symptoms

All AEs spontaneously reported by the patient or reported in response to the open question from the study personnel: 'Have you had any health problems since the previous visit/you were last asked?', or revealed by observation will be collected and recorded in the CRF. When collecting AEs, the recording of diagnoses is preferred (when possible) to recording a list of signs and symptoms. However, if a diagnosis is known and there are other signs or symptoms that are not generally part of the diagnosis, the diagnosis and each sign or symptom will be recorded separately.

6.3.7 Adverse events based on examinations and tests

The results from protocol-mandated laboratory tests and vital signs measurements will be summarized in the CSR. Deterioration as compared to baseline in protocol-mandated laboratory values and vital signs should therefore only be reported as AEs if they fulfill any of the SAE criteria or are the reason for discontinuation of treatment with the IPs.

If deterioration in a laboratory value or vital sign is associated with clinical signs and symptoms, the sign or symptom will be reported as an AE and the associated laboratory result or vital sign will be considered as additional information. Whenever possible, the reporting Investigator should use the clinical rather than the laboratory term (eg, anemia versus low hemoglobin value). In the absence of clinical signs or symptoms, clinically relevant deteriorations in non-mandated parameters should be reported as AEs.

Deterioration of a laboratory value that is unequivocally due to disease progression should not be reported as an AE/SAE.

Any new or aggravated clinically relevant abnormal medical finding at a physical examination as compared with the baseline assessment will be reported as an AE.

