5.2.2 Physical examination, vital signs and medical history

At screening and baseline, a complete physical examination (including body weight and height) will be performed and include an assessment of the following: general appearance, respiratory, cardiovascular, abdomen, skin, head and neck (including ears, eyes, nose and throat), lymph nodes, thyroid, musculo-skeletal (including spine and extremities) and neurological systems. After baseline, only targeted physical examination (including body weight) is necessary.

Physical examination information will only be reported in the CRF if abnormalities are reported as AEs. For information on how AEs based on physical examination should be recorded and reported, see Section 6.3.

Findings from medical history and physical examination will be given a baseline grade according to the procedure for AEs. Increases in severity of pre-existing conditions during the

study will be considered AEs, with resolution occurring when the grade returns to at or below the pre-study baseline.

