Additional laboratory tests (where clinically indicated only)	Free tri-iodothyronine (T3) and free thyroxine (T4) ^c , creatinine clearance, alkaline phosphatase (ALP), autoimmune antibody test ^d					
(a) Tests for urine bilirubin and urobilinogen will be done (per institutional standard method) at baseline only, and repeated only as clinically indicated.						
	At screening only, for the evaluation of eligibility criteria.					
	If TSH is abnormal or there is clinical suspicion of an AE related to the endocrine system					
	then free T3 and free T4 testing will be done.					
thyroiditis,	If a patient experiences an AE that is thought to be possibly of autoimmune nature (eg thyroiditis, pancreatitis, hypophysitis, or diabetes insipidus), the Investigator should collect a blood sample for appropriate autoimmune antibody testing by a local laboratory.					

The hematology and clinical chemistry should be performed at a local laboratory at or near to the Investigator site. Urinalysis should be performed at a local laboratory (at or near to the Investigator site) or by dip-stick per institutional care. Tests for urine bilirubin and urobilinogen will be done (per institutional standard method) at baseline only, and repeated only as clinically indicated.

Sample tubes and sample sizes may vary depending on laboratory method used and routine practice at the site. Clinically significant (as assessed by the Investigator) laboratory abnormalities will be recorded in the CRF as AEs. Laboratory results relevant to / associated with AESIs will be recorded in the CRF.

Additional safety samples may be collected during the study if clinically indicated at the discretion of the Investigator and according to standard medical practice. The Investigator should make an assessment of the available results with regard to clinically relevant abnormalities. The laboratory results should be signed and dated, and retained at center as source data for laboratory variables. For information on how AEs based on laboratory tests

Note: In case a patient shows an AST or ALT \geq 3 ULN or total bilirubin \geq 2 ULN please refer to APPENDIX D for further instructions (also see Section 6.3.8).

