3. PRIMARY AND SECONDARY VARIABLES

3.1 Safety

The primary outcome measure for the study is the number and proportion of patients with AESI. Pre-defined Medical Dictionary for Regulatory Activities (MedDRA) preferred terms groupings will be used to identify AESI.

'On treatment' will be defined as assessments between date of first dose and 90 days following last dose inclusive.

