3.1.1.2 Other Significant Adverse Events

During the evaluation of the AE data, a medically qualified expert will review the list of AEs that were not reported as SAEs and 'Discontinuation of Investigational Product due to Adverse Events' (DAEs). Based on the expert's judgment, significant AEs of particular

clinical importance may, after consultation with the Global Patient Safety Physician, be considered other significant adverse events (OAEs) and reported as such in the Clinical Study Report (CSR). A similar review of laboratory/vital signs/ECG data will be performed for identification of OAEs.

Examples of these are marked hematological and other laboratory abnormalities, and certain events that lead to intervention (other than those already classified as serious) or significant additional treatment.

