- At least one treatment-emergent serious AESI
- At least one treatment-emergent AESI by maximum NCI CTCAE grade
- At least one treatment-emergent AESI causally related to study medication
- At least one treatment-emergent AESI with fatal outcome
- At least one treatment-emergent AESI which required additional treatment with steroids, immunosuppressants and hormone replacement therapy
- Laboratory findings, vital signs and other safety parameters associated with AESI will be summarised as part of the AESI outcome measures.

Length of intervention with steroids, immunosuppressants and/or hormone replacement therapy for AESIs will be calculated based on treatment start and stop dates. Total treatment

times will then be combined for each patient and summarised for patients experiencing at least one treatment-emergent AESI.

The exact 95% CIs around the incidence estimates will also be reported for each AESI type.

A summary of total duration (days) of AESI will be provided. For ongoing AESI, the date of death or data cut-off will be imputed as end date.

Immuno-mediated adverse events

Summaries of treatment-emergent imAEs by AESI category and PT will include number (n) and percentage (%) of patients who have:

- At least one treatment-emergent imAE
- At least one treatment-emergent imAE by outcome
- At least one treatment-emergent imAE leading to treatment interruption or discontinuation
- At least one treatment-emergent serious imAEs
- At least one treatment-emergent imAE by maximum NCI CTCAE grade
- At least one treatment-emergent imAE causally related to study medication
- At least one treatment-emergent imAE with fatal outcome

Subgroup analyses

Subgroup analyses will be conducted for the summary of TEAEs in the following subgroups of the SS:

- Sex (male versus female)
- Age at baseline: <65 vs 65-74 vs ≥75 years of age). This will be determined from the date of birth (BRTHDAT in the DM domain) and baseline visit (VIS_DAT in the VISIT domain) on the eCRF. Patients with a partial date of birth (ie for those countries where year of birth only is given) will have an assumed date of birth of 1st Jan [given year]). Patients with a missing age value will be included using the mean age and categorised accordingly.
- Race: Asian vs non-Asian
- ECOG performance status at baseline: 0-1 vs 2
- Tumor histology: Urothelial (i.e. TCC) vs non-urothelial

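### Protocol Sections 5.3.1 and 6.3.7 disagree on whether a laboratory-only deterioration in a mandated test is an AE, and no planned table shows how many such deteriorations have no matching AE or AESI

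*Protocol*

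**What the plan says.** Protocol Section 5.3.1 states: "Clinically significant (as assessed by the Investigator) laboratory abnormalities will be recorded in the CRF as AEs". It makes no exception for scheduled tests and does not limit the rule to serious or treatment-ending events. It adds: "Laboratory results relevant to / associated with AESIs will be recorded in the CRF". Its closing pointer on laboratory-based AEs is incomplete in the available text, but the parallel sentence in Section 5.2.2 reads: "For information on how AEs based on physical examination should be recorded and reported, see Section 6.3".

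Protocol Section 6.3.7 starts from the premise that results of mandated tests will be summarised in the CSR. It concludes that deteriorations in them "should therefore only be reported as AEs if they fulfill any of the SAE criteria or are the reason for discontinuation of treatment". Symptom-free, clinically relevant changes are to be AEs only for parameters that are not mandated. It also says: "Deterioration of a laboratory value that is unequivocally due to disease progression should not be reported as an AE/SAE".

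The tests concerned are mandated. Protocol Table 3 puts creatinine, total bilirubin, AST, ALT, TSH, lipase and amylase in the routine chemistry panel, Table 2 schedules chemistry at every treatment visit, and Section 5.3.1.1 requires TSH at all visits.

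For the primary outcome, SAP Section 3.1 says that predefined MedDRA "preferred terms groupings will be used to identify AESI". SAP Section 4.2.1 plans laboratory shift tables, ULN-multiple tables, TSH shifts and, in the AESI part: "Laboratory findings, vital signs and other safety parameters associated with AESI will be summarised as part of the AESI outcome measures". SAP Section 3.1.1.2 adds, for other significant AEs (OAEs): "A similar review of laboratory/vital signs/ECG data will be performed for identification of OAEs".

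**The concern.** Whether a rise in ALT becomes an AE should not depend on which section of the protocol the site coordinator reads. If it does, the same clinical picture is counted at one site and not at another, and the pooled incidence follows neither rule. Two secondary objectives (Protocol Section 2.2) rest on AE records: the incidence and nature of treatment-emergent AEs, and interruption or discontinuation because of them. The SAP also reports dose interruptions due to AEs separately from those due to other reasons. A laboratory-only rise that leads to a held dose could fall on either side of that split.

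The primary outcome could also be reached, because an event that is never recorded as an AE has no preferred term and cannot enter an AESI grouping.

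**Working it through.** No rate in the documents allows a size to be calculated, so the check is a comparison of the texts.

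**Step 1. Where the rules conflict.** Take a deterioration that the Investigator judges clinically significant.

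| Situation | Section 5.3.1 | Section 6.3.7 | Conflict |
|---|---|---|---|
| Mandated test, meets an SAE criterion (including potential Hy's Law cases reported as SAEs) | AE | AE | No |
| Mandated test, reason for discontinuing treatment | AE | AE | No |
| Mandated test, with signs or symptoms | AE | The sign or symptom is the AE | No; an AE is recorded either way |
| Mandated test, leading to a diagnosis | AE | Diagnosis recorded (Section 6.3.6) | No |
| Non-mandated test, no symptoms | AE | AE if clinically relevant | No |
| Mandated test, no symptoms or diagnosis, not serious, dosing continues | AE | Not an AE | **Yes** |
| As the row above, but a dose is interrupted | AE | Not an AE | **Yes** |

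The last row reads discontinuation as stopping treatment. Protocol Section 2.2 supports this, since it names interruption and discontinuation separately.

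**Step 2. Secondary outcomes.** SAP Section 4.2.1 tabulates all TEAEs, TEAEs leading to dose interruption, and interruptions by AE versus other reason. The two conflicting rows enter or leave these tables according to the rule a site followed. This holds whatever the AESI groupings contain.

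**Step 3. Primary outcome.** AESIs come from preferred-term groupings (SAP Section 3.1). For the interim and final analyses, imAEs add a programmatic check for steroid, immunosuppressant or hormone treatment (SAP Section 3.1.1.1), applied to potential imAEs. If a grouping includes laboratory terms, the conflicting events are eligible under 5.3.1 and lost under 6.3.7. If it does not, nothing changes under either rule. The groupings are not in the available text. The current AESI descriptions (Protocol Sections 2.1 and 6.5, SAP Section 3.1.1.1) name hepatitis, nephritis and pancreatitis without the associated laboratory increases, which points towards a small or zero effect.

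**Step 4. Could a planned output show the gap?**
- Shift, ULN-multiple and TSH tables: they show the abnormality, but are not split by whether an AE or AESI was reported.
- Laboratory findings associated with AESI: the summary starts from AESIs already reported, so it cannot show a deterioration without one.
- OAE review: it leads to a causality table (other significant TEAEs related to study medication), but only for events classed as OAEs.
- Liver narratives: combined ALT or AST and bilirubin elevations only.

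**Step 5. The plan's own figure.** SAP Section 1.3 gives over 75% probability of at least ten events for an AESI of true incidence 1% with 1200 patients. P(X ≥ 10) = 1 − Σ C(1200, x) × 0.01^x × 0.99^(1200 − x), summed over x = 0 to 9, gives 0.759. The SAP figure is reproduced, and nothing here shows it to be wrong.

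**The case against.** The strongest reply is that Section 6.3.7 is a deliberate and specific rule. Mandated results are summarised in the CSR, so they need not be duplicated as AEs, and the SAP delivers those summaries in detail. If the broken pointer in Section 5.3.1 leads to Section 6.3, the specific rule governs the general sentence and a clarifying clause would do. What is left out is by construction non-serious, symptom-free, undiagnosed and not treatment-ending. The SAP also provides for a further medical review of AESI terms before database lock and allows extra safety tables.

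Much of this stands. It narrows the point to the two conflicting rows and makes an effect on the AESI count unproven. It does not remove the flat instruction in 5.3.1 to record such abnormalities as AEs, which a site can follow in good faith. The reviews and optional tables are not a specified comparison of laboratory worsening with AE reporting.

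It is also fair to object that the proposed table cannot by itself separate few events from unrecorded ones: an abnormality without an AE may be due to progression or may have been judged not clinically significant. That is why it should be labelled descriptive.

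**Conclusion.** The contradiction is real, and it bears directly on TEAE incidence and on interruptions attributed to AEs. The direction is known: following 6.3.7 gives fewer AEs than following 5.3.1. The size is not, because the documents give neither the frequency of such deteriorations nor the rule sites used. It is worth fixing because the remedy is cheap and determines what the AE counts can be taken to mean.

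A reader might infer three stronger things that the documents do not support.
- That the primary AESI proportion is understated. This requires laboratory terms in groupings that cannot be seen, and the current AESI wording leans the other way.
- That the SAP's 75% assurance fails. If 10%, 20%, 30% or 50% of a 1% AESI went unrecorded, the probability of ten or more recorded events would be 0.638, 0.491, 0.334 or 0.083. Every one of those shares is an assumption, applied to a generic AESI rather than a laboratory-based one. They are not evidence of a defect.
- That laboratory data are nowhere linked to AESIs or to causality. Both links exist, but only for AESIs already reported and for events classed as OAEs.

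**What to change.** 1. **Recording rule.** Reconcile Sections 5.3.1 and 6.3.7 into one rule for mandated laboratory values. If data collection is at or past cut-off, leave ascertainment unchanged and state in the CSR which rule applied, and that AE, AESI and AE-related interruption counts may omit laboratory-only events. The Protocol synopsis estimates final cut-off for Q2 2020 and SAP amendment v2.0 is dated 12 June 2020, so the CSR statement is the realistic route. Cost: one sentence in the protocol or a short statement in the CSR.

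2. **One supportive table.** First confirm that laboratory data are complete in the database, because Protocol Section 4 says not everything is entered in the CRF and Section 5.3.1 singles out AESI-related results. Then cross-tabulate treatment-emergent worsening from baseline, by worst on-treatment CTCAE grade, for ALT, AST, bilirubin, creatinine, lipase and amylase against a matching AE or AESI reported or not. For TSH, use a shift from within to outside the project reference range, so that patients eligible with stable treated hypothyroidism whose TSH is already outside the range at baseline are not flagged. Label the table as descriptive. Footnote that changes unequivocally due to progression are not AEs, and that the not-reported column is not a count of missed AESIs. Cost: one extra table from data already planned for summary, with no new data collection.
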